17. ADVERSE EXPERIENCE AND COMPLICATION REPORTING

Throughout the course of the proposed study, all efforts will be made to remain alert to possible adverse experiences or untoward findings. If adverse experiences occur, the first concern will be the safety and welfare of the subject and appropriate medical intervention will be made. Any adverse experiences observed by the investigator or reported by the subjects, whether or not ascribed to the investigational procedure or device, will be recorded on the subject's adverse event case report form. A new adverse event case report form is used for each adverse event or adverse event-related visit.

Any serious adverse events (SAEs) and unanticipated adverse device events (UADE), whether ascribed to the investigational device or not, will be communicated as soon as possible to OnPoint Vision Inc. and to the IRB. These reports must be confirmed in writing within 5 working days of learning of the occurrence. Any subjects who are terminated from the study due to adverse experiences will be followed and documented until their medical outcome is determined, and a written report provided to OnPoint Vision Inc. by the investigator.

18. CONCOMITANT MEDICATIONS/THERAPY

The investigator may prescribe medications and therapy as deemed beneficial for the subject.

19. DATA COLLECTION

Data will be collected using case report forms (see Appendix 8). Completed case report forms will be scanned to the sponsor within seven days of the study visit.

19.1. Device Accountability

The Investigator will be responsible for keeping current and accurate records of the amount of Intraoperative Implantable Pseudophakic Contact Lenses (IOPCLs) received, implanted, and disposed/returned. The IOPCLs must be stored in a secure area and are to be implanted only in subjects enrolled in the study, in accordance with the conditions specified in this protocol. Accountability records will include.

- The lot numbers/serial numbers of the lenses received, the receipt date, and the quantity received
- The names of the people who received, used, or disposed of the lenses.
- A record of each subject implanted with the lenses.
- o Quantity of IOPCLs returned at the completion of enrollment.

19.2. Protocol Deviations

Protocol deviations will be grouped based on severity. Major/Important deviations are a subset of protocol deviations that might significantly affect the completeness, accuracy, and/or reliability of the study data or that might significantly affect a subject's rights, safety, or well-being. For example, important protocol deviations might include enrolling subjects in violation of key eligibility criteria designed to ensure a specific subject population or failing to collect data necessary to interpret primary endpoints, as this may compromise the scientific value of the trial. Protocol deviations will be grouped by type will be recorded.

19.3. Study Completion Procedures

19.3.1. Subject Completion

Subjects are considered to have completed the study if they have completed all follow-up examinations through 330-420 days (12 months) including post-removal examinations.

19.3.2. Subject Termination

Subjects may be terminated from the study at the discretion of the Investigator only for reasons related to the study treatment regimen that would jeopardize their health and/or welfare if they were to continue in the study. Terminated subjects will not be replaced. However, every effort will be made to follow terminated subjects for safety reasons using the appropriate case report forms until the planned end of the study period.

19.3.3. Subject Discontinuation

Subjects may be discontinued from the study for non-treatment-related reasons only when no other option is possible. Reasons for discontinuation include, but are not necessarily limited to, 1) voluntary withdrawal from the study by the subject; 2) subject has moved from the area and is determined to be lost to follow-up; 3) subject is unwilling or unable to cooperate with study requirements (non-compliance with post-operative follow-up visits, etc.).

Prior to discontinuing a subject, every effort should be made to contact the subject in an effort either to get the subject back into compliance with the protocol or to obtain as much follow-up data as possible regarding the subject's current visual status.

20. DATA REPORTING

A Case Report Form binder will be provided by the Sponsor for each subject who is enrolled in the study. The appropriate case report form will be completed and signed by the Investigator/examiner at each examination. All case report forms will be completed in a legible manner in ink. Any corrections will be made by drawing a single line through the incorrect entry and initialing and dating the change. Information transferred from the source document will be faxed to the sponsor.

All forms will be reviewed for completeness and evident recording errors will be rectified by contact with the appropriate persons at the clinical site. Corrective and preventative actions will be implemented to avoid repeat errors. Double entry routines will be used to minimize data entry errors, and computerized editing routines will be used to identify unusual data entries for verification prior to statistical analysis. Data analysis will be performed per the statistical analysis plan in Appendix 6.

21. RECORDING OF DATA AND RETENTION OF DOCUMENTS

Subject data will be documented in an anonymous fashion and the subject will be identified by the subject enrollment number. If, as an exception, it is necessary for safety or regulatory reasons to identify the subject, the Sponsor or its representative and the Investigator are bound to keep this information confidential.

The Investigator must retain essential documents indefinitely after the completion of the study, unless otherwise notified by the Sponsor. The Investigator agrees to adhere to the document retention procedures when signing the protocol Investigator statement of approval.

Essential documents include but are not limited to the following:

- IRB approvals for the study protocol, all amendments and informed consent form(s)
- IRB annual study review,
- Subject's signed informed consent form,

- Correspondence from and to the Sponsor, and
- Any other documents relevant to the conduct of the study.

22. STUDY MONITORING

OnPoint Vision Inc. personnel (or designees) will monitor all clinical studies in a manner consistent with good clinical practices (GCPs) and all applicable health authority regulations, and in accordance the study monitoring plan. Study monitoring will involve the following elements.

- 1. OnPoint Vision Inc. personnel (or designee) will meet with the investigator(s) prior to the initiation of the study in order to review the adequacy of the subject population, facilities, and equipment with respect to the needs of the study, and to familiarize the investigator with the study protocol.
- 2. OnPoint Vision Inc. personnel (or designee) will meet with the investigator(s) at the time study subjects begin to be enrolled in order to ensure that subjects are being properly selected and that study data are being correctly recorded.
- 3. OnPoint Vision Inc. personnel (or designee) may remotely review and audit or visit the clinical site at any time during the study to review the case report forms and verify data against medical records.
- Interim monitoring visits and telephone consultation will occur as necessary during the course of the study to ensure the proper progress and documentation of the study findings.

Sponsor field staff under the supervision of the investigator will periodically visit investigational sites to ensure that study procedures (e.g., refractions, visual acuity measurements) are performed consistently and in compliance with protocol-specified techniques, and in doing so may come in direct contact with study subjects.

The rights and well-being of subjects are protected, and the study is being conducted in accordance with 21CFR, Parts 50, 54, 56 and 812.42 (U.S.C 282(j)). ISO 14155 (2011) Clinical investigation of Medical Devices for Human Subjects, ISO 11979-7, and applicable local regulations and the ethical principles laid down in the Declaration of Helsinki (see Appendix 4).

During the course of the study, if an Investigator is determined to be non-compliant with the study plan and/or applicable regulatory requirements, the Sponsor will take action to secure compliance. In addition, the Sponsor may terminate the Investigator's participation in the study if appropriate or the Investigator remains non-compliant despite the Sponsor's actions.

22.1. Remote Study Monitoring – COVID-19

Per FDA Guidance on Conduct of Clinical Trials of Medical Products during COVID-19 Public Health Emergency (May 14, 2020, updated January 27, 2021), remote study monitoring will be

implemented due to the COVID-19 pandemic. On-Point personnel will contact sites via email and telephone to review study procedures, trial participant status, and study progress.

Remote monitoring procedures are being implemented on a larger scale as clinical research sites or study personnel are not comfortable with allowing on-site monitoring visits due to the increased risk of infection. Additionally, travel restrictions have further restricted access to clinical sites and the ability to perform on-site monitoring visits. These expanded remote monitoring guidelines may be continued through study completion, even after the COVID-19 issues are resolved.

The goal of remote monitoring is consistent with all monitoring, in that it is to assure that the rights and safety of all subjects are protected and ensure the quality and integrity of the data.

The On-Point monitor will provide the clinical site with a list of documents requested based on queries or data pending review. These documents will be uploaded to a secure site which is HIPPA compliant. The site will upload the necessary source documents to the monitor for review. Any documents uploaded to the monitor must have all subject identifiers (e.g. subject name, initials, date of birth) redacted. No additional personnel or email addresses should be copied on this correspondence from the site.

The monitor may request documents from the Regulatory binder for review, but a full regulatory document review will be done at an on-site visit after restrictions have been lifted and monitors are allowed back into the practices.

On-Point will carefully document situations where monitors were unable to access, or had to delay monitoring of a clinical site. On-Point personnel and monitors will document protocol deviations, or other GCP non-compliance issues identified at the clinical sites and whether delayed identification was due to postponed monitoring.

Remote monitoring activities, including remote review of source documents, will be documented in the same level of detail as on-site monitoring activities, and any resulting actions to address issues identified from the remote source document review should be consistent with procedures and processes described in this monitoring plan.

23. CONFIDENTIALITY

All study data generated as a result of this study will be regarded as confidential, until appropriate analysis and review by the Sponsor or its designee and the Investigator(s) are completed. The results of the study may be published or presented by the Investigator(s) after the review by, and in consultation and agreement with, the Sponsor, and such that confidential or proprietary information is not disclosed. Prior to publication or presentation, a copy of the final text should be forwarded by the Investigator(s) to the

Sponsor, or its designee, for comment. Such comments shall aim to ensure the scientific integrity of the proposed publications and/or presentations and ensure that the data and material referring to OnPoint Vision Inc. products and activities receive fair, accurate, and reasonable presentation.

24. APPENDICES

Appendix 1 – Informed Consent Document

Appendix 2A – Schedule of Visits and Procedures

Appendix 2B – Schedule of Visits and Procedures after IOPCL AMD-MAG Removal

Appendix 3 – Clinical Methods

Appendix 4 – Declaration of Helsinki

Appendix 5 – Investigators Responsibility with Clinical Trial Agreement

Appendix 6 – Statistical Analysis Plan

Appendix 7 – VFQ-25 Questionnaire

Appendix 8 – Case Report Forms

## LIST OF ABBREVIATIONS

**UBM** 

AE Adverse event

ANOVA Analysis of variance

BCDVA Best corrected distance visual acuity
BCNVA Best corrected near visual acuity

CI Confidence interval
CS Contrast sensitivity
CSR Clinical study report
EFS Early feasibility study

ETDRS Early Treatment Diabetic Retinopathy Study

Ultrasound biomicroscopy

IOP Intraocular pressure

IOPCL Intraocular pseudophakic contact lens
MRSE Manifest refraction spherical equivalent

OCT Optical Coherence Tomography
PCIOL Pseudophakic intraocular lens
SAP Statistical Analysis Plan

UCDVA Uncorrected distance visual acuity
UCNVA Uncorrected near visual acuity
VFQ-25 Visual Function Questionnaire-25

#### 1 INTRODUCTION

This Statistical Analysis Plan (SAP) outlines the statistical methods to be implemented within the scope of Protocol IOPCL AMD-20, entitled "Early Feasibility Study to Evaluate the Safety and Effectiveness of the IOPCL AMD-MAG for Secondary Implantation in the Capsular Bag to Improve Near Vision in Subjects with Age-Related Macular Degeneration after Cataract Surgery." Results of the proposed analyses will become the basis of the clinical study report for this protocol.

The purpose of this plan is to provide specific guidelines from which the analysis will proceed. All planned analyses specified in this document will be performed. Any changes to this plan, in the form of "post hoc" or "data driven" analyses will be identified as such in the final clinical study report. Any changes will either be reflected in amendments to this plan before the database lock or specifically documented in the clinical study report.

## 2 STUDY OBJECTIVE

The primary objective of this study is to determine the stability of the IOPCL AMD-MAG to successfully adhere to a pseudophakic intraocular lens without rotation or slippage.

The secondary objective of this study is to determine if the IOPCL-AMD-MAG can improve uncorrected near visual acuity in subjects previously implanted with an Alcon SN60WF, SA60AT or SA60WF monofocal intraocular lens.

#### 3 STUDY ENDPOINTS

# 3.1 Effectiveness Endpoint

## 3.1.1 Primary Effectiveness Endpoint

The primary effectiveness endpoint identified for this Early Feasibility Study for IOPCL AMD-MAG is:

• Proportion of eyes (≥ 75%) able to achieve 10 letters or more of uncorrected near visual acuity (at 14 cm) at 12 months from baseline.

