4.3. Primary Effectiveness Endpoint

Proportion of eyes ($\geq 75\%$) able to achieve improvement of 10 letters or more of uncorrected near visual acuity (at 14 cm) at 12 months from baseline.

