4.4 Secondary Effectiveness Endpoints

- Proportion of eyes (≥ 50%) able to achieve improvement of 20 letters or more of uncorrected near visual acuity (at 14 cm) at 12 months from baseline.
- Proportion of eyes (≥ 75%) able to achieve improvement of 10 letters or more when comparing uncorrected near visual acuity (UCNVA) (at 14 cm) at 12 months from baseline BCNVA (at 30 cm, wearing the appropriate preoperative distance refractive correction in addition to +3.0D add).
- Proportion of eyes (≥ 50%) able to achieve improvement of 20 letters or more when comparing uncorrected near visual acuity (UCNVA) (at 14 cm) at 12 months from baseline BCNVA (at 30 cm, wearing the appropriate preoperative distance refractive correction in addition to +3.0D add).
- Proportion of eyes (≥ 75%) able to achieve improvement of 10 letters or more when comparing best corrected near visual acuity (BCNVA) (at 14 cm) at 12 months from baseline BCNVA (at 30 cm, wearing the appropriate preoperative distance refractive correction in addition to +3.0D add).
- Proportion of eyes (≥ 50%) able to achieve improvement of 20 letters or more when comparing best corrected near visual acuity (BCNVA) (at 14 cm) at 12 months from baseline BCNVA (at 30 cm, wearing the appropriate preoperative distance refractive correction in addition to +3.0D add).

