## 3.1.2 Secondary Effectiveness Endpoints

The secondary effectiveness endpoints identified for this Early Feasibility Study for IOPCL AMD-MAG are:

- Proportion of eyes (≥ 50%) able to achieve 20 letters or more of uncorrected near visual acuity (at 14 cm) at 12 months from baseline.
- Proportion of eyes (≥75%) able to achieve improvement of 10 letters or more when comparing uncorrected near visual acuity (UCNVA) (at 14 cm) at 12 months from baseline BCNVA (at 30 cm, wearing the appropriate preoperative distance refractive correction in addition to +3.0D add).

- Proportion of eyes (≥50%) able to achieve improvement of 20 letters or more when comparing uncorrected near visual acuity (UCNVA) (at 14 cm) at 12 months from baseline BCNVA (at 30 cm, wearing the appropriate preoperative refractive distance correction addition to +3.0D add).
- Proportion of eyes (≥ 75%) able to achieve improvement of 10 letters or more when comparing best corrected near visual acuity (BCNVA) (at 14 cm) at 12 months from baseline BCNVA (at 30 cm, wearing the appropriate preoperative distance refractive correction in addition to +3.0D add).
- Proportion of eyes (≥ 50%) able to achieve improvement of 20 letters or more when comparing best corrected near visual acuity (BCNVA) (at 14 cm) at 12 months from baseline BCNVA (at 30 cm, wearing the appropriate preoperative distance refractive correction in addition to +3.0D add).

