## 7.4 Effectiveness Analysis

## 7.4.1 Primary Analyses of the Primary Effectiveness Endpoint

The proportion of eyes able to achieve 10 letters or more of uncorrected near visual acuity (at 14 cm) at 12 months from baseline will be summarized.

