# 7.4.2 Primary Analyses of the Secondary Effectiveness Endpoints

The proportion of eyes able to achieve 20 letters or more of uncorrected near visual acuity (at 14 cm) at 12 months from baseline will be summarized.

- Change in UCNVA from baseline will be reported in lines including the following bins: loss of 15 or more letters, loss of 10 or more letters, loss of more than 5 letters, no change (within +/- 5 letters), gain of more than 5 letters, gain of 10 or more letters, gain of 15 or more letters, gain of 20 or more letters.
- The UCNVA value of the implanted eyes will be summarized descriptively by mean, standard deviation, median, minimum, and maximum at 1 month or later.

The proportion of eyes able to achieve 10 letters or more of uncorrected near visual acuity (at 14 cm) at 12 months from baseline BCNVA (at 30 cm, wearing the appropriate preoperative distance refractive correction in addition to +3.0D add).

• Change in UCNVA from baseline BCNVA will be reported in lines including the following bins: loss of 15 or more letters, loss of 10 or more letters, loss of more than 5 letters, no change (within +/- 5 letters), gain of more than 5 letters, gain of 10 or more letters, gain of 15 or more letters, gain of 20 or more letters.

The proportion of eyes able to achieve 20 letters or more of uncorrected near visual acuity (at 14 cm) at 12 months from baseline BCNVA (at 30 cm, wearing the appropriate preoperative distance refractive correction in addition to +3.0D add).

• Change in UCNVA from baseline BCNVA will be reported in lines including the following bins: loss of 15 or more letters, loss of 10 or more letters, loss of more than 5 letters, no

change (within +/- 5 letters), gain of more than 5 letters, gain of 10 or more letters, gain of 15 or more letters, gain of 20 or more letters.

The proportion of eyes able to achieve 10 letters or more of best corrected near visual acuity (at 14 cm) at 12 months from baseline BCNVA (at 30 cm, wearing the appropriate preoperative distance refractive correction in addition to +3.0D add).

• Change in BCNVA from baseline will be reported in lines including the following bins: loss of 15 or more letters, loss of 10 or more letters, loss of more than 5 letters, no change (within +/- 5 letters), gain of more than 5 letters, gain of 10 or more letters, gain of 15 or more letters, gain of 20 or more letters.

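### The SAP's primary responder rule omits the words that make it a gain, so it conflicts with the protocol and can be read as an absolute level of 10 letters

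*SAP*

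**What the plan says.** Protocol 4.3 sets the primary effectiveness endpoint as the proportion of eyes, with a target of at least 75%, "able to achieve improvement of 10 letters or more of uncorrected near visual acuity (at 14 cm) at 12 months from baseline". Protocol 4.4 sets the first secondary endpoint in the same form, with a target of at least 50%: eyes "able to achieve improvement of 20 letters or more of uncorrected near visual acuity (at 14 cm) at 12 months from baseline".

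SAP 3.1.1 keeps the 75% target but describes eyes "able to achieve 10 letters or more of uncorrected near visual acuity (at 14 cm) at 12 months from baseline". The first bullet of SAP 3.1.2 describes eyes "able to achieve 20 letters or more of uncorrected near visual acuity (at 14 cm) at 12 months from baseline". In both, the word improvement is gone.

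The analysis sections carry the same text. SAP 7.4.1 consists of one sentence, which begins "The proportion of eyes able to achieve 10 letters or more of uncorrected near visual acuity (at 14 cm" and says that this proportion will be summarized. SAP 7.4.2 opens with "The proportion of eyes able to achieve 20 letters or more of uncorrected near visual acuity (at 14 cm".

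The other four secondary endpoints in SAP 3.1.2 do speak of improvement, measured against baseline best corrected near acuity (BCNVA) at 30 cm with a +3.0D add. When 7.4.2 restates those four, the word is missing there too.

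**The concern.** Protocol section 20 sends the data analysis to the SAP, so the SAP sentence is the one a programmer will code. The two documents give different text for the primary effectiveness rule. The SAP text, read on its own, is met by any eye that scores 10 letters at 12 months, whatever it scored before surgery. Such a rule could credit the device with successes that involve no change.

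The study is unmasked, has no control group and includes at most 10 eyes. Its responder rule should need no interpretation once data are visible, and an analysis at 4-6 months is planned before the final one.

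**Working it through.** The documents give no power, alpha or sample-size calculation for this endpoint, so there is no planned figure to reproduce. The check compares the texts and then works out when the two readings differ.

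**1. The texts side by side**

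| Endpoint | Protocol | SAP definition | SAP analysis |
|---|---|---|---|
| Primary, 10 letters UCNVA | 4.3: improvement stated | 3.1.1: omitted | 7.4.1: omitted |
| First secondary, 20 letters UCNVA | 4.4: improvement stated | 3.1.2, first bullet: omitted | 7.4.2, first sentence: omitted |
| Other four secondary, against baseline BCNVA | 4.4: improvement stated | 3.1.2: stated | 7.4.2: omitted |

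**2. What the rest of the SAP implies**

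- SAP 2 states the UCNVA objective as an improvement.
- SAP 7.4.2 uses the short form for four endpoints that 3.1.2 defines as gains.
- SAP 7.4.2 tabulates change in UCNVA, with a bin for gains of at least 10 letters.
- SAP 7.4.4, which does present absolute levels, words them as a score or better and has a lowest category below 40 letters. No 10-letter or 20-letter level appears there.
- SAP 8.1 declares no switch from gain to level.

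All of this points to a gain. None of it is in 7.4.1.

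**3. When the two readings differ**

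Let b be the baseline and y the 12-month UCNVA letter score, both at 14 cm.

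- Protocol rule: y − b ≥ 10.
- Literal SAP rule: y ≥ 10.

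Since b ≥ 0, any eye that meets the protocol rule also meets the literal rule. The literal rule is therefore never stricter. The readings disagree exactly when 10 ≤ y < b + 10. The smallest change that passes the literal rule is 10 − b.

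The documents give no baseline UCNVA, so the values of b below are assumptions.

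| Assumed b | Change needed, protocol | Change needed, literal SAP (10 − b) | Unchanged eye passes literal rule? |
|---|---|---|---|
| 0 | +10 | +10 | no |
| 5 | +10 | +5 | no |
| 10 | +10 | 0 | yes |
| 20 | +10 | −10 | yes |
| 30 | +10 | −20 | yes |

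At b = 30, an eye that falls to 12 letters (change 12 − 30 = −18) still passes the literal rule. For the 20-letter endpoint the same algebra applies with 20 in place of 10, so an unchanged eye passes from b = 20 upward.

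**4. What it could do to the 75% target**

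With 10 evaluable eyes the target is 0.75 × 10 = 7.5, so 8 eyes are needed. With 9, 8, 7 or 6 evaluable eyes it is 7, 6, 6 or 5. The exact binomial chance of at least 8 successes in 10, for assumed responder rates, is:

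| Assumed rate | P(at least 8 of 10) |
|---|---|
| 0.60 | 0.167 |
| 0.75 | 0.526 |
| 0.90 | 0.930 |
| 0.95 | 0.988 |

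These show how sensitive the target is to the choice of rule. They do not predict the rate under either rule.

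**The case against.** The strongest reply is that the SAP means a gain and any informed reader will see it. Both UCNVA sentences still end with a reference to baseline, which does no work if an absolute level is meant. Step 2 of the working adds more evidence on the same side. The bins in 7.4.2 will also produce the protocol's quantity in any case, because SAP 1 commits to performing every planned analysis. Finally, the study is descriptive, its primary objective is lens stability rather than acuity, and no error rate is affected.

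Most of this stands. A reader might infer that the SAP has replaced the protocol's endpoint with an absolute level, and the documents do not support that. A reader might also infer that success could approach 100% with no device effect. That requires most eyes to start at or above 10 letters, and nothing in the documents says so. Uncorrected testing at 14 cm, in eyes with monofocal lenses, a refraction within 1 D of zero and corrected distance acuity of 20/80 to 20/800, could well give lower baselines.

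Two things remain. The reference to baseline does not settle the matter, because the phrase can also be read as fixing the time point. And the clarifying bins are listed under a secondary endpoint, while the primary analysis section has no responder definition of its own.

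**Conclusion.** The point holds as a conflict of wording in the operative primary effectiveness rule. The SAP omits the words that make the criterion a gain, in both definition and analysis, for the primary and the first secondary endpoint. Intent is very probably a gain, but the controlling sentence can be read as a level and 7.4.1 contains nothing to rule that out.

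The size is conditional on baseline UCNVA at 14 cm: nil near 0 letters, partial between 0 and 10, and enough to pass an unchanged eye from 10 letters upward. With 8 of 10 eyes needed, a few such eyes could decide whether the target is met. Sample size and error rates are unaffected, since none are specified for this endpoint. It should be corrected before the analysis is programmed.

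**What to change.** Restore the words *improvement of* in SAP 3.1.1, the first bullet of 3.1.2, 7.4.1 and every restatement in 7.4.2.

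For the primary and first secondary endpoints only, add a responder definition: 12-month UCNVA letters minus preoperative UCNVA letters, both at 14 cm, of at least 10 (primary) or at least 20 (first secondary).

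Do not carry that formula into the other four secondary endpoints. Their comparator is baseline BCNVA at 30 cm with the +3.0D add, and two of them have BCNVA as the 12-month outcome. A UCNVA-minus-UCNVA formula would misdefine them and contradict Protocol 4.4, so they need only the missing words and their stated comparator.

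The cost is SAP wording, which SAP 1 allows to be amended before database lock. No new data, visits or subjects are needed, and the targets of 75% and 50% stay as they are.
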